#### 9.4.3.2 Secondary Efficacy Analyses

Once the primary hypothesis is rejected for the primary endpoint, the secondary variables will be tested using a fixed sequence testing procedure as follows:

- For US (FDA) submission: Proportion of subjects with mean Hb level during the evaluation period defined as Week 28 until Week 52  $\geq 10.0$  g/dL.
- EU regulatory submission: Hemoglobin (Hb) response, defined as mean Hb during Weeks 28 to 36 within the range of 10.0 to 12.0 g/dL without having received rescue therapy within 6 weeks prior to and during this 8-week evaluation period.

The hypothesis to be tested for the first secondary efficacy analysis is:

H0: Hb response rate for subjects in the roxadustat group - Hb responder rate for subjects in the epoetin alfa group  $\leq -15\%$

Versus

H1: Hb response rate for subjects in the roxadustat group - Hb responder rate for subjects in the epoetin alfa group  $> -15\%$ .

A 2-sided 95% CI for the difference of two responder rates (roxadustat-ESA) based on the Miettinen and Nurminen approach adjusting for treatment group and other stratification factors will be calculated and H0 will be rejected if the lower bound of the 95% CI is greater than  $-15\%$ .

- The average monthly iron use during Weeks 1 to 36 will be compared between the 2 treatment groups using an ANCOVA model with BL iron replete as a covariate, and treatment arm and randomization stratification factors as fixed effects. Superiority will be declared if the lower bound of the 2-sided 95% CI of the difference between epoetin alfa and roxadustat exceeds 0.
- The change in low-density lipoprotein (LDL) cholesterol averaged over Weeks 12 to 28 from BL will be analyzed using an MMRM model with BL LDL cholesterol as a covariate and treatment arm, visit, interaction of treatment arm and visit, and randomization stratification factors as fixed effects. Superiority will be declared if the lower bound of the 2-sided 95% CI of the difference between epoetin alfa and roxadustat exceeds 0.
- Time to exacerbation of BP will be analyzed using the Cox Proportional Hazards model adjusting for treatment arm and randomization stratification factors. Superiority of roxadustat vs. epoetin alfa will be declared if the upper bound of the 2-sided 95% CI of the hazard ratio is  $< 1$ .

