##### 3.2.2 Secondary Efficacy Endpoints

The secondary efficacy endpoints in this study are:

- US (FDA) submission: Proportion of subjects with mean Hb level during the evaluation period defined as Week 28 until Week 52  $\geq 10.0$  g/dL.
- EU regulatory submission: Hemoglobin (Hb) response, defined as mean Hb during Weeks 28 to 36 within the target range of 10.0 to 12.0 g/dL without having received rescue therapy within 6 weeks prior to and during this 8-week evaluation period.
- Average monthly IV iron use per subject during Weeks 1 to 36 (monthly defined as a period of 4 weeks).
- Change from BL in low-density lipoprotein (LDL) cholesterol to the average LDL cholesterol of Weeks 12 to 28
- Change from BL in SF-36 Physical Functioning (PF) subscore to the average PF subscore of Weeks 12 to 28
- Change from BL in SF-36 Vitality (VT) subscore to the average VT subscore of Weeks 12 to 28
- Effect on predialysis BP:
  - Time to an exacerbation of hypertension from BL during Weeks 1 to 36

- An increase from BL of  $\geq 20$  mm Hg systolic blood pressure (sBP) and sBP  $> 170$  mmHg

OR

- An increase from BL of  $\geq 15$  mm Hg diastolic blood pressure (dBP) and dBP  $> 100$  mmHg
- Change from BL in mean arterial pressure (MAP) to the MAP value averaged over Weeks 20 to 28

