4.2 Secondary Efficacy Endpoints

The secondary efficacy endpoints in this study are as below for both US and Ex-US submission unless otherwise specified:

- US (FDA) submission: Proportion of subjects with mean hemoglobin level during the evaluation period defined as Week 28 until Week 52 ≥ 10.0 g/dL.
- Ex-US submission: Proportion of subjects with hemoglobin response, defined as mean hemoglobin during Weeks 28 to 36 within the target range of 10.0 to 12.0 g/dL without having received rescue therapy within 6 weeks prior to and during this 8-week evaluation period.
- Change from baseline in Low Density Lipoprotein (LDL) cholesterol to the average LDL cholesterol of weeks 12 to 28.
- Hemoglobin change from baseline to the average level during the Weeks 18 to 24 for subjects with baseline hs-CRP $>$ ULN.
- Average monthly IV iron use per subject during the Treatment Period during Weeks 28 to 52 (monthly defined as a period of 4 weeks).
- Time to first RBC Transfusion during the treatment
- Change from BL in mean arterial pressure (MAP) to the MAP value averaged over weeks 20 to 28
- Time to first exacerbation of hypertension: An increase from BL of ≥ 20 mm systolic blood pressure (SBP) and SBP ≥ 170 mmHg or an increase from baseline of ≥ 15 mmHg diastolic blood pressure (DBP) and DBP ≥ 100 mmHg during Weeks 28 to 52.

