5.3 Methodology and Conventions

Continuous variables will be presented by descriptive statistics: n, mean, standard deviation, median, minimum, and maximum. Categorical variables will be tabulated by frequency count and percentage. For efficacy endpoints, the standard error and 95% confidence intervals (CI) will be presented as part of the descriptive summaries.

Safety and efficacy data will be summarized and presented by treatment group and time point in summary tables.

Lab results obtained from the central laboratory will be used for all efficacy and safety analyses. Local laboratory values, if collected in the CRF's, will be listed only in data listing. Unless otherwise stated, all statistical tests will be two-sided hypothesis tests performed at the 5% level of significance for main effects and all confidence intervals will be two-sided 95% confidence intervals.

The secondary endpoints will be tested sequentially using the fixed sequence approach for multiplicity adjustments at an alpha level of 0.05. There will be no adjustments for multiple comparisons for other tests.

All analyses will be performed using SAS® Version 9.1.3 or higher.

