11.2.2.5 Time to first RBC Transfusion

Time to the first RBC transfusion during treatment will be analyzed and compared between the 2 treatment groups using the Cox Proportional Hazards model adjusting for baseline Hb, treatment group and stratification factors.

Non-inferiority of roxadustat vs. Epoetin will be declared if the upper bound of the 2-sided 95% confidence interval of the hazard ratio is less than 1.8 and superiority.

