11.2.2.7 Blood pressure increase

- Time to first exacerbation of hypertension During Weeks 28 to 52

Time to first exacerbation during weeks 28 to 52 will be analyzed and compared between the 2 treatment groups using the Cox Proportional Hazards model adjusting for treatment group and stratification factors.

Superiority of roxadustat vs. Epoetin will be declared if the upper bound of the 2-sided 95% confidence interval of the hazard ratio is less than 1.

Subjects will be censored at the time of the last available blood pressure if an exacerbation in blood pressure does not occur.

Sensitivity analysis will be performed on proportion of subjects with increase in blood pressure at any time during the study, defined as an increase from baseline of ≥ 20 mm Hg systolic BP and sBP >170 mmHg or an increase from baseline of ≥ 15 mm Hg diastolic BP and dBP >100 mmHg. Increases from baseline in blood pressure are considered as confirmed by taking the mean of triplicates. The proportion of subjects with increase in blood pressure will be compared between the 2 treatment groups using logistic regression model adjusting for baseline predialysis systolic and diastolic BP as covariates and treatment group and stratification factors as fixed effects.

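### The Cox model for time to first hypertension exacerbation omits baseline blood pressure; adding it is a free improvement with a modest gain in power and robustness

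*Protocol*

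**What the plan says.** Protocol 3.2.2 lists as a secondary endpoint "Time to an exacerbation of hypertension from BL during Weeks 1 to 36". An event is a systolic rise of at least 20 mmHg to above 170, or a diastolic rise of at least 15 mmHg to above 100. SAP 4.2 and Table 6 move the window to Weeks 28 to 52 and make the cut-offs inclusive; the systolic part reads "An increase from BL of ≥ 20 mm systolic blood pressure (SBP) and SBP ≥ 170 mmHg".

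The model is the same in both documents. Protocol 9.4.3.2: "Time to exacerbation of BP will be analyzed using the Cox Proportional Hazards model adjusting for treatment arm and randomization stratification factors". SAP 11.2.2.7: "using the Cox Proportional Hazards model adjusting for treatment group and stratification factors". The randomization factors (Protocol 9.2) are screening Hb, cardiovascular, cerebrovascular or thromboembolic history, prior epoetin dose and region. The list in SAP 11.1.1.1 has incident-dialysis status in place of region. None is a pressure measure.

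The test is confirmatory. SAP 5.3: "The secondary endpoints will be tested sequentially using the fixed sequence approach for multiplicity adjustments at an alpha level of 0.05". Protocol 9.4.3.2 sets the rule: "Superiority of roxadustat vs. epoetin alfa will be declared if the upper bound of the 2-sided 95% CI of the hazard ratio is" below 1. SAP Table 6 makes it Test 7 of 7 and adds non-inferiority with a margin of 1.8.

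Elsewhere the plan does use the relevant baseline value. In SAP 11.2.2.7 the sensitivity analysis of the proportion with exacerbation uses a "logistic regression model adjusting for baseline predialysis systolic and diastolic BP as covariates and treatment group and stratification factors as fixed effects". The transfusion test in SAP 11.2.2.5 uses a "Cox Proportional Hazards model adjusting for baseline Hb, treatment group and stratification factors". The MAP and LDL models include baseline MAP and baseline LDL.

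**The concern.** Baseline pressure enters the event definition twice: it sets how far pressure must rise, and it sets how far the subject starts from the cut-off. It should therefore predict the event well. Leaving a strong predictor out of a Cox model brings the estimated hazard ratio closer to 1, costs some power, and lets a chance difference in starting pressure feed into the treatment comparison. At stake is a superiority claim at the end of the SAP's sequence. In the order listed in Protocol 9.4.3.2, MAP and the two SF-36 tests come after it, so a missed rejection there would also stop three later tests. No reason for the omission is given, and the SAP's own logistic analysis shows that baseline pressure is regarded as relevant.

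**Working it through.** **1. The plan's only power figure.** Protocol 9.1 claims at least 99% power for the primary Hb non-inferiority test. Inputs: 300 per arm, SD 1.25, margin 0.75, true difference −0.30 (as in the synopsis and SAP 5.1).

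- SE = 1.25 × √(2/300) = 0.1021
- z = (0.75 − 0.30)/0.1021 = 4.41
- Power = Φ(4.41 − 1.96) = 0.993, so the claim is reproduced.

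No event rate, hazard ratio or power is given for the hypertension endpoint, so steps 2 to 4 rest on assumed inputs.

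**2. Power with and without baseline pressure.** Visit-level systolic and diastolic pressures were simulated for 600 subjects, 1:1. The visits follow the documents: 16 for Weeks 1–36 (Weeks 1 and 2, eleven visits from Week 4 to 24, then 28, 32, 36) and 7 for Weeks 28–52. The cut-offs were taken in the strict form. Cox models were fitted without baseline pressure, with linear baseline systolic and diastolic terms, and with quadratic terms added, using 4,000 replicates. Assumed systolic inputs (mean / between-subject SD / visit SD / true-change SD, mmHg): A 140/18/14/10; B 148/20/14/10; C 140/22/12/8; D 145/16/18/12.

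| Window, set | Assumed shift (mmHg) | Events of 600 | HR without → linear | Power % without → linear → quadratic |
|---|---|---|---|---|
| Weeks 1–36, A | −5 | 173 | 0.667 → 0.646 | 75.1 → 80.3 → 82.4 |
| Weeks 1–36, B | −5 | 212 | 0.676 → 0.661 | 81.3 → 84.6 → 86.2 |
| Weeks 1–36, C | −5 | 124 | 0.601 → 0.578 | 80.2 → 84.9 → 87.4 |
| Weeks 1–36, D | −5 | 294 | 0.742 → 0.731 | 72.6 → 76.5 → 78.4 |
| Weeks 28–52, A | −5.5 | 121 | 0.612 → 0.599 | 75.8 → 79.0 → 80.3 |
| Weeks 28–52, B | −5 | 155 | 0.656 → 0.646 | 73.6 → 76.6 → 77.9 |
| Weeks 28–52, C | −5 | 85 | 0.570 → 0.556 | 69.8 → 73.3 → 75.0 |
| Weeks 28–52, D | −5.5 | 218 | 0.703 → 0.697 | 73.8 → 76.2 → 77.2 |

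Linear terms gain 3.3 to 5.2 points (Weeks 1–36) or 2.4 to 3.5 points (Weeks 28–52). With quadratic terms the gains are 4.9 to 7.3 and 3.4 to 5.2.

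Cross-check by Schoenfeld's formula, Φ(|ln HR| × √(E/4) − 1.96), first row without baseline: 0.405 × √(173/4) = 2.66, and Φ(0.70) = 0.76, against 75.1% simulated.

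**3. A smaller treatment effect.** Assumed: systolic mean 145 (SD 18), diastolic 76 (SD 11), systolic visit SD 12–18, baseline the mean of three visits, shift −2 systolic and −1 diastolic. With 1,500 replicates:

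- Weeks 28–52: 21.1 → 22.3%, 18.7 → 19.9%, 19.1 → 20.9%
- Weeks 1–36: 25.5 → 27.3%, 23.9 → 25.3%, 27.5 → 29.1%

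The gain is 1.2 to 1.8 points. Taking both sets of inputs, linear terms gain about 1 to 3.5 points in the SAP window and about 1.5 to 5 in the protocol window.

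**4. Chance imbalance and type I error.** The SD of the between-arm difference in baseline systolic pressure is about √(18² + 14²/3) × √(2/300) = 19.7 × 0.0816 = 1.6 mmHg for set A with a three-reading baseline. Across the sets it was 1.5–1.9. Each 1 mmHg moved the unadjusted log hazard ratio by 0.017–0.033 (0.015–0.033 including the smaller-effect inputs). For set A, Weeks 1–36, one SD gives 0.031 × 1.60 = 0.050, about 5% on the hazard ratio.

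Under no treatment effect (6,000 replicates per scenario):

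| | Unadjusted | Linear adjustment |
|---|---|---|
| Two-sided type I error, all replicates | 3.9–4.8% | 4.0–5.4% |
| False favourable result when roxadustat starts more than 1 SD lower (nominal 2.5%) | 4.1–8.0% | 1.6–3.2% |

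The stratification factors were not simulated.

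**The case against.** The strongest reply is that the unadjusted Cox test is a valid test and this is a preference about efficiency. That stands: overall type I error is not inflated, and dependence on baseline imbalance is conditional on the randomization that happens to be drawn. The adjusted and unadjusted hazard ratios are also different quantities, so part of the movement away from 1 is non-collapsibility and not the removal of an error.

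The gain is small, and its size rests on assumed inputs. With a −2 mmHg effect it is 1 to 2 points on a test with about 20–30% power. The larger gains belong to Weeks 1–36, which SAP 4.3 moves to additional efficacy; the SAP's controlled test covers Weeks 28–52 and no later test depends on it. The comparison also left out the strata. If cardiovascular history or ESA dose tracks blood pressure, the gain over the planned model shrinks by an unknown amount. All of this limits the size. None of it is a reason to leave the covariates out.

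A reader might infer that this is the only key secondary test without its baseline value. The documents do not support that: the Hb responder comparison in SAP 11.2.2.1 adjusts only for treatment and strata, and the IV iron model uses baseline iron repletion status rather than prior iron use. A reader might also infer that the Cox and logistic results cannot be compared because their covariates differ. The logistic analysis also differs in window (any time in the study), cut-off (strict) and model, so matching the covariates removes only one of several differences.

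**Conclusion.** The omission is real and appears in both documents. It is a missed free improvement, not a validity error; a reading that the planned test is biased or has inflated error is not supported by the check. Under the assumed pressure distributions, with 600 subjects and strata ignored, omitting linear baseline terms costs about 1 to 3.5 power points in the SAP window and about 1.5 to 5 in the protocol window. It also leaves the hazard ratio open to shifts of roughly 0.015–0.033 on the log scale per mmHg of chance systolic imbalance. The direction was the same in every scenario with a treatment effect. The size is uncertain, and the gain over the planned stratified model could be smaller.

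**What to change.** In Protocol 9.4.3.2 and SAP 11.2.2.7, add baseline predialysis systolic and diastolic pressure as continuous covariates in the Cox model for time to first exacerbation, using the pre-dose mean that SAP 5.4 already defines. Quadratic or spline terms are worth considering. The relation is partly non-monotone, because a subject with a low baseline must climb to the cut-off while one with a high baseline must rise a further 20 mmHg. Choose the form in advance. Make the same change in the supportive Cox models of SAP 11.3.5 (time to hypertension adverse event and to intensification of antihypertensive therapy), whose logistic counterparts already include these covariates.

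Add one sentence saying that the hazard ratio compared with 1, and with the 1.8 non-inferiority margin in Table 6, is the covariate-adjusted one.

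Cost: wording only. Blood pressure is already measured at both screening visits and on Day 1. Because the study is open-label, the change should be fixed before baseline pressure is examined by arm, so that it cannot look like a response to an observed imbalance.

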#### 9.4.4 Safety Analyses

The Safety analyses will be performed using the safety analysis set (SAF).

Safety parameters include adverse events, SAEs, laboratory parameters, vital signs, ECG parameters, and PE.

The number and percentage of subjects reporting TEAEs and TESAEs in each treatment group will be tabulated. Descriptive statistics will be presented for laboratory, vital signs values and ECG parameters by visit and for the changes from BL to each visit.

The CV safety assessment of roxadustat will also be based on pooled analysis of composites of adjudicated CV events pooled across multiple global Phase 3 clinical studies which includes this study, according to the regional pooled SAPs for meeting regional regulatory requirements.

For US (FDA) submission only: The primary safety endpoint in this study is the MACE (Major Adverse Cardiac Event) composite endpoint, defined as time to first occurrence of death from all causes, MI, or stroke, only for the purpose of being pooled across multiple similar studies in the Phase 3 program. None of the individual studies are powered to meet the MACE primary safety endpoint individually. The pooled MACE analysis is only for purposes of supporting a US FDA regulatory filing of roxadustat.

Safety data and dosing decisions will be monitored on an ongoing basis. Ongoing review of safety data will be conducted by an independent DSMB.

For each safety parameter, the last assessment made prior to the first dose of study medication will be used as the BL for all analyses of that safety parameter.

#### **9.4.4.1 Adverse Events**

Adverse events will be coded using the Medical Dictionary for Regulatory Activities (MedDRA).

An AE (classified by preferred term) occurring during the Treatment Period will be considered a treatment emergent AEs (TEAE) if it was not present prior to the first dose of study medication, or if it was present prior to the first dose of study medication but increased in severity during the Treatment Period. An AE that occurs more than 28 days after the ET/EOT Visit date will not be counted as a TEAE.

The number and percentage of subjects reporting TEAEs in each treatment group will be tabulated by system organ class and preferred term; by system organ class, preferred term, and severity; and by system organ class and preferred term. If more than one event occurs with the same preferred term for the same subject, the subject will be counted only once for that preferred term using the most severe and most related occurrence for the summarization by severity and by relationship to the study medication.

The overall distribution of TEAEs by severity and relationship to study medication will be summarized by treatment group.

The proportion of subjects with TESAE, fatal SAEs (ie, events that caused death), and AEs leading to permanent discontinuation of study medication will be summarized by System Organ Class (SOC), preferred term and treatment group

Treatment emergent adverse events of interest will also be reported in terms of incidence rate per Patient Exposure Year (PEY).

Listings will be presented of subjects with SAEs, subjects with AEs leading to discontinuation, and subjects who died.

#### **9.4.4.2 Clinical Laboratory Parameters**

Descriptive statistics for laboratory values and changes from BL at each assessment time point will be presented by treatment group for each laboratory parameter. To assess potentially clinically meaningful laboratory abnormalities, the number and percentage of subjects with post-BL lab values outside a predefined range or limit of change will be tabulated by treatment group.

### 9.4.4.3 Vital Signs

Descriptive statistics for vital signs (systolic and diastolic BP, pulse rate, respiration rate) and their changes from BL at each visit and, the EOS will be presented by treatment group.

### 9.4.4.4 Electrocardiogram

Descriptive statistics for ECG parameters (eg, HR, PR interval, QRS interval, QT interval, QTc interval) at BL and changes from BL at each assessment time point will be presented by treatment group. To assess potentially clinically meaningful ECG abnormalities, the number and percentage of subjects with post-BL ECG values outside a predefined range or limit of change will be tabulated by treatment group, as well as shift tables for results of ECG interpretation (normal, abnormal not significant, abnormal significant).

## 9.5 Interim Data Cut

There are currently no plans to conduct an interim data cut.

Safety data and dosing decisions will be monitored on an ongoing basis. Additional ongoing review of safety data will be conducted by an independent DSMB (see Section 4.8).

## 9.6 Statistical Analysis Plan

The Statistical Analysis Plan (SAP) will provide details of the data analyses. As an open-label study the SAP will be finalized prior to accumulation of a substantial amount of data to ensure lack of bias. Any significant changes to the analyses described in this protocol will be highlighted in the SAP and detailed in the Clinical Study Report.

## 9.7 Protocol Deviations

A protocol deviation is generally an unplanned excursion from the protocol that is not implemented or intended as a systematic change. The investigator is responsible for ensuring the study is conducted in accordance with the procedures and evaluations described in this protocol and must protect the rights, safety, and welfare of subjects. The investigator should not implement any deviation from, or changes of, the protocol, unless it is necessary to eliminate an immediate hazard to trial subjects.

Due to the unique nature of this study, following issues are not to be considered as protocol deviations:

- Given the complexity in EPO dose adjustments and the need to take into account the various clinical parameters in EPO dose titration, one would not consider it a protocol deviation when patients are dosed according to local standard of care whether or not it is concordant with package insert/SmPC
- Given the complexity in Roxadustat dose adjustments and the need to take into account the various clinical parameters in Roxadustat dose titration, one would not consider it a protocol deviation when subjects are dosed based on their clinical circumstances whether or not it is concordant with the Roxadustat dose adjustment guidelines unless it was related to “excessive hematopoiesis” (Hb  $\geq$ 13 g/dL, requires a dose-hold) or “Overdose” (prescribed  $>$ 3.0 mg/kg per dose or 400 mg per dose, whichever is lower)

- ESA administrations in Roxadustat subjects during hospitalization are not to be reported as protocol deviation, if the roxadustat dosing were not allowed or available during that hospitalized period
- IV iron administrations in study subjects during hospitalization are not be reported as protocol deviation

For the purposes of this protocol, protocol deviations requiring notification to the Sponsor will be defined and detailed in the study monitoring plan.

